12.1.2. Serious Adverse Events

12.1.2.1. Assessment of Serious Adverse Events

An AE is considered serious if it fulfills one or more of the following criteria:

- Death (i.e., the AE caused or led to death).
- It was life threatening (i.e., immediately life-threatening).
- It required or prolonged inpatient hospitalization.
- It resulted in a persistent or significant disability/incapacity (i.e., the AE resulted in a substantial disruption of the subject's ability to carry out normal life functions).

- It resulted in a congenital anomaly/birth defect in the offspring of a study subject who was exposed to study therapy prior to conception or during pregnancy.
- It is a medically significant event(s), which may include “sight-threatening events,” that may not meet any of the above serious criteria but may jeopardize the subject or require medical or surgical intervention to prevent one of the outcomes listed above.

12.1.2.2. Reporting Serious Adverse Events

The SAE eCRF must be completed with as much information as is available within 24 hours of knowledge of the event.

To improve the quality and precision of acquired SAE data, Investigators should observe the following guidelines:

- Death: Death is an outcome of an event. The event that resulted in the death should be recorded and reported as the SAE.
- Hospitalizations for Surgical or Diagnostic Procedures: The illness leading to the surgical or diagnostic procedure should be recorded as the SAE, not the procedure itself. The procedure should be captured in the case narrative as part of the action taken in response to the illness.

Depending on the nature and seriousness of the AE, Santen may request additional documentation, for example, copies of the ophthalmic and medical records as well as results of laboratory tests. If the subject was hospitalized, a copy of the discharge summary may be requested.

12.1.2.3. Expedited Reporting of Serious Adverse Events

Santen (or designee) will provide the Principal Investigator with a reporting cover letter and a masked expedited safety report for expedited reporting of SAEs to the IRB or IEC. The Principal Investigator is responsible for receiving and reviewing expedited safety reports, submitting expedited safety reports to the IRB or IEC, and maintaining copies of expedited safety reports in the study records.

12.1.3. Events of Special Interest

The following are considered ESIs and should be reported on the appropriate eCRF with as much information as available within 24 hours of knowledge of the event:

- Pregnancy:
 - There are no controlled data with the investigational product in human pregnancy. It is required that females of childbearing potential use effective contraception during the study and recommended for 4 weeks for female subjects of childbearing potential and 12 weeks for male subjects capable of fathering children after the completion of the study. Any pregnancy occurring during study treatment should be reported and the subject will be discontinued from the study. The subject should be followed until the end of pregnancy or until the end of the study, whichever is longer.

- Medication administration errors
 - Study medication administration errors determined to be **significant** by the Investigator will be reported and evaluated as ESIs. Examples of study medication administration errors may include, but are not limited to: incorrect dose of study medication and administration of study medication from an incorrect kit. An AE does not necessarily need to have occurred to count as a study medication administration error. A medication administration error is an unintended failure in the process of treatment with a medicinal product that leads to, or has the potential to lead to harm of the subject.
- Macular edema (including cystoid macular edema):
 - Macular edema has been reported in some patients during the DE-117 clinical trials. Any cases of macular edema (including cystoid macular edema) should be reported in the ESI form in eCRF, or in case the EDC system is down, in the manual ESI form. Any cases of macular edema (including cystoid macular edema) will need to be followed until the event is determined to be resolved, irreversible, chronic, stable, the subject withdraws consent, or no further information can be reasonably obtained as per [Section 12.1.4](#).

12.1.4. Follow-up of Adverse Events

All reported AEs should be followed until resolution or until the subject's participation in the study ends. Subjects with the following types of events should be followed by the Investigator until the event is determined to be resolved, irreversible, chronic, stable, the subject withdraws consent, or no further information can be reasonably obtained.

- On-going SAEs issued after study medication treatment
- On-going ESIs, including pregnancy, medication errors resulting in AE's, and macular edema/cystoid macular edema issued after study medication treatment
- Early termination and withdrawal from the study due to study medication related AEs

In addition, on a case by case basis, Santen (or designee) may request follow up beyond the scheduled exit visit.

The follow-up information on an individual SAE or AE (or ESI) will be entered into the eCRF prior to database lock. If the information requested by Santen is not part of the eCRF, or when database lock has already been completed, the site's response to follow-up requests should be emailed to [contact] or reported in writing and fax to [contact] (in the US).

12.1.5. Manual Back-Up Reporting Procedures

This study is utilizing an EDC system for data entry. In the event that the EDC system is unavailable for electronic reporting, the manual back-up reporting procedures below should be followed.

- Complete an AE Form, SAE Form, pregnancy Form, medication error Form, or ESI Form as appropriate.

- Attach a cover sheet with your contact information and address to Santen (or its designee).
- Email (preferred) or Fax the cover sheet and the completed form(s) to Santen (or its designee) at [contact] or [contact] (in the US).

When the EDC system becomes available, the EDC system should be updated with all previously reported information.

12.2. Safety Parameters

In addition to observed values, changes from baseline will be evaluated at relevant post baseline visits. For a safety outcome measure, the baseline value will be the last observation of that outcome measure prior to the first dose of study medication.

12.2.1. Ocular Assessments

Ocular assessments include:

- BCVA
- Slit-lamp biomicroscopy findings: anterior chamber cells, anterior chamber flare, lid hyperemia, lid edema, conjunctival hyperemia, conjunctival chemosis, corneal edema, corneal staining, keratic precipitate, lens, anterior synechiae of iris and posterior synechiae of iris
- Ophthalmoscopy variables: glaucomatous optic nerve
- Iris color/eyelash/eyelid

12.2.2. Non-ocular Assessments

Non-Ocular assessments include:

- Blood pressure and pulse rate

13. OTHER ASSESSMENTS

13.1. Demographic, Baseline Characteristics and Other Assessments

Subject demographics, baseline characteristics, medical history, concomitant medications, exposure to study medication, and pregnancy test for females of childbearing potential will be summarized.

14. STATISTICAL METHODS

This section outlines topics related to the statistical methods used in the design and analysis of the study. A more detailed description of all the analyses and methods is provided in the Statistical Analysis Plan (SAP).

14.1. Interim Analysis

There is no planned interim analysis for this study.

14.2. Final Analysis

An unmasked final analysis will be performed after all subjects completed Month 3. The analysis will evaluate the efficacy and safety of DE-117 Ophthalmic Solution 0.002% once daily compared with Timolol Maleate Ophthalmic Solution 0.5% twice daily.

Another analysis will be performed after all subjects completed Month 12. The analysis will evaluate the long term efficacy and safety of DE-117 Ophthalmic Solution 0.002% once daily.

14.3. General Considerations

Descriptive statistics, unless otherwise noted, will include the number of subjects (N), mean, standard deviation (SD), median, minimum, and maximum for continuous variables and N and percent for categorical variables.

The study eye will be defined as the eye that qualifies per inclusion criteria at Baseline (Visit 2). For example, for adult subjects, IOP must be ≥ 22 mmHg at all IOP measurement time-points (08:00, 10:00 and 16:00). See [Section 8.1](#) and [Section 8.2](#) for all inclusion/exclusion criteria. If both eyes qualify, the eye with the higher mean diurnal IOP at Baseline (Visit 2) will be the study eye. If both eyes have the same mean diurnal IOP at baseline, then the right eye will be designated as the study eye.

Statistical analyses for pediatric subjects may be performed separately depending on the number of pediatric subjects enrolled in this study.

More details on the statistical methods will be described in SAP which will be finalized prior to unmasking the data.

14.3.1. Sample Size

The sample size calculation was based on a two-sided Type I error rate of 5% and a non-inferiority margin of 1.5 mmHg. Assuming a between-treatment difference of 0 mmHg, SD of 4.0 mmHg and a correlation coefficient of 0.6 among repeated measures, approximately 400 adult subjects in total (200 subjects per treatment arm) will provide 90% power to demonstrate non-inferiority of DE-117 Ophthalmic Solution 0.002% to Timolol Maleate Ophthalmic Solution 0.5%.

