2. SYNOPSIS

Name of Sponsor/Company:

Santen Inc.
[name]
[name], USA

Name of Investigational Product: DE-117 Ophthalmic Solution**Name of Active Ingredient:**

Glycine, *N*-[6-[[[4-(1*H*-pyrazol-1-yl)phenyl]methyl](3-pyridinylsulfonyl)amino]methyl]-2-pyridinyl]-, 1-methylethyl ester
Propan-2-yl 2-[[6-[(4-pyrazol-1-ylphenyl)methyl-pyridin-3-ylsulfonylamino]methyl]pyridin-2-yl]amino]acetate

Title of Study: A Phase III, Randomized, Double-Masked, Active-Controlled, Parallel-Group, Multi-center Study Assessing the Efficacy and Safety of DE-117 Ophthalmic Solution 0.002% Compared with Timolol Maleate Ophthalmic Solution 0.5% in Subjects with Glaucoma or Ocular Hypertension - Spectrum 3 Study

Protocol Number: 011709IN

Number of Subjects (planned): Approximately 400 adult subjects (200 in each treatment arm) with Open-Angle Glaucoma (OAG) or Ocular Hypertension (OHT) and up to 30 pediatric subjects (15 in each treatment arm) with pediatric glaucoma or OHT will be randomized in this study.

Number of Sites (planned): Approximately 35 Sites

Study Period: Approximately 19 months

Phase of Development: Phase III

Primary Objective:

To determine whether DE-117 Ophthalmic Solution 0.002% given once daily is non-inferior to Timolol Maleate Ophthalmic Solution 0.5% given twice daily in reducing the intraocular pressure (IOP) in subjects with glaucoma or OHT after 3 months of treatment

Secondary Objectives:

To determine whether DE-117 Ophthalmic Solution 0.002% is non-inferior to Timolol Maleate Ophthalmic Solution 0.5% in reducing mean diurnal IOP in subjects with glaucoma or OHT after 3 months of treatment

To determine whether DE-117 Ophthalmic Solution 0.002% is superior to that of Timolol Maleate Ophthalmic Solution 0.5% in reducing mean diurnal IOP in subjects with glaucoma or OHT after 1 week of treatment

Safety Objective:

To determine the safety of DE-117 Ophthalmic Solution 0.002% as compared to Timolol Maleate Ophthalmic Solution 0.5% in subjects with glaucoma or OHT

Duration of Treatment:

[figure not shown]
Adult subjects : 12 months (3-month double-masked treatment plus 9-month open-label treatment)

Pediatric subjects : 3 months (3-month double-masked treatment)**Methodology:**

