Safety will be assessed by adverse events (AEs), BCVA, slit-lamp biomicroscopy, ophthalmoscopy, iris color/eyelash/eyelid examination, resting blood pressure and pulse rate.

Other:

Subject demographics, baseline characteristics, medical history, concomitant medications,

exposure to study medication, and pregnancy for females of childbearing potential will be summarized.

Efficacy Endpoints:

Primary Efficacy Endpoint

The primary efficacy endpoint is the IOP in the study eye measured at the specified time points: 08:00, 10:00 and 16:00 at Week 1, Week 6 and Month 3 (Visits 3, 4 and 5).

Key Secondary Efficacy Endpoints

- Mean diurnal IOP in the study eye at Month 3 (Visit 5)
- Mean diurnal IOP in the study eye at Week 1 (Visit 3)

Other Secondary Efficacy Endpoints

- Change and percent change from baseline in IOP at each timepoint/post-baseline visit
- Change and percent change from baseline in mean diurnal IOP at each post-baseline visit
- Having a mean diurnal IOP reduction $\geq 20\%$, $\geq 25\%$, or $\geq 30\%$ from Baseline (Visit 2) at each post-baseline visit
- Having a mean diurnal IOP ≤ 18 mmHg at each post-baseline visit

Safety Endpoints

Safety will be evaluated by the following parameters:

- Incidence of ocular and systemic AEs
- Blood pressure and pulse rate
- BCVA
- Slit-lamp biomicroscopy findings: anterior chamber cells, anterior chamber flare, lid hyperemia, lid edema, conjunctival hyperemia, conjunctival chemosis, corneal edema, corneal staining, keratic precipitates, lens, anterior synechiae of iris, posterior synechiae of iris
- Ophthalmoscopy
- Iris color/eyelash/eyelid

Statistical Methods:

The sample size calculation was based on a two-sided Type I error rate of 5% and a non-inferiority margin of 1.5 mmHg. Assuming a between-treatment difference of 0 mmHg, a standard deviation (SD) of 4.0 mmHg, and a correlation coefficient of 0.6 among repeated measures, approximately 400 adult subjects in total (200 subjects per treatment arm) will provide 90% power to demonstrate non-inferiority of DE-117 Ophthalmic Solution 0.002% to Timolol Maleate Ophthalmic Solution 0.5%.

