14.3.2. Statistical Hypotheses and Level of Significance

The primary efficacy endpoint is the IOP in the study eye measured at the specified time points: 08:00, 10:00 and 16:00 at Week 1, Week 6 and Month 3 visits.

For the primary endpoint, a Mixed Effect Model for Repeated Measurement (MMRM) will be used to test the following hypotheses:

$$H_0: \mu_T - \mu_C > \Delta \text{ versus } H_A: \mu_T - \mu_C \leq \Delta$$

where μ_T and μ_C denote the mean values of the primary endpoint in DE-117/Vehicle arm and Timolol Maleate arm, respectively, and Δ denotes the non-inferiority margin of 1.5 mmHg.

Treatment difference between the DE-117/Vehicle arm and Timolol Maleate arm at each specified time point of each post-baseline visit up to Month 3 will be reported along with 95% confidence intervals. Non-inferiority is established if the upper limit of the two-sided 95% confidence interval for the difference in the mean IOP (0.002% DE-117 - Timolol Maleate) is ≤ 1.5 mmHg at all nine time points and ≤ 1.0 mmHg in majority (5 or more) of the time points. If the upper limit of the 95% confidence interval for the difference is ≤ 0 at all nine time points, superiority of DE-117 to Timolol will be claimed.

If non-inferiority in the primary endpoint is achieved, then the following two key secondary endpoints will be tested sequentially according to hierarchical fixed sequence procedure:

1. Mean diurnal IOP in the study eye at Month 3

The corresponding hypothesis is:

$$H_{0S1}: \mu_{Ts1} - \mu_{Cs1} > \Delta \text{ versus } H_{AS1}: \mu_{Ts1} - \mu_{Cs1} \leq \Delta$$

where μ_{Ts1} and μ_{Cs1} denote the mean diurnal IOP at Month 3 in DE-117/Vehicle arm and Timolol Maleate arm, respectively; and Δ denotes the non-inferiority margin of 1.5 mmHg.

If the hypothesis is rejected at 0.05 significance level, then the following key secondary endpoint will be tested:

2. Mean diurnal IOP in the study eye at Week 1

The corresponding hypothesis is:

$$H_{0S2}: \mu_{Ts2} = \mu_{Cs2} \text{ versus } H_{AS2}: \mu_{Ts2} \neq \mu_{Cs2}$$

Where μ_{Ts2} and μ_{Cs2} denote the mean diurnal IOP at Week 1 in DE-117/Vehicle arm and Timolol Maleate arm, respectively.

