### **3.3. Sample Size Planning**

The sample size calculation was based on a two-sided Type I error rate of 5% and a non-inferiority margin of 1.5 mmHg. Assuming a treatment difference of 0 mmHg between the DE-117 arm and the Timolol arm, a standard deviation (SD) of 4.0 mmHg, and a correlation coefficient of 0.6 among repeated measures, approximately 400 adult subjects in total (200 subjects per treatment arm) will provide 90% power to demonstrate noninferiority of DE-117 Ophthalmic Solution 0.002% to Timolol Maleate Ophthalmic Solution 0.5% in IOP-lowering effect. Up to 30 pediatric subjects will be enrolled with the agreement from FDA.

The standard deviation of 4.0 mmHg was determined from previous DE-117 studies conducted in the United States: 33-002 and 33-003.

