### **5.3. Full Analysis Set**

The Full Analysis Set (FAS) will include all randomized subjects who received at least one dose of study medication and provided Baseline IOP data (at any timepoint) and at least one post-baseline IOP measurement (at any timepoint). Efficacy analyses will be performed using the FAS and summarized by treatment as randomized.

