### 8.1. Efficacy Analyses for Double-Masked Period

#### 8.1.1. Analyses of Primary Endpoint and Key Secondary Endpoints

##### 8.1.1.1. Primary Analyses

###### 8.1.1.1.1. Primary Endpoint

The primary efficacy endpoint is IOP in the study eye at each scheduled timepoint (08:00, 10:00, and 16:00) at each of three follow-up visits, Week 1, Week 6, and Month 3. The nine combinations of three scheduled timepoints at each of three follow-up visits are referred to subsequently as nine timepoints. For the primary endpoint, the following null (versus alternative) hypothesis will be tested:

$$H_0: \mu_T - \mu_C > \Delta \text{ for at least one timepoint}$$

versus

$$H_A: \mu_T - \mu_C \leq \Delta \text{ at all nine timepoints}$$

where  $\mu_T$  and  $\mu_C$  denote the mean values of the primary endpoint in the DE-117 arm and the Timolol arm, respectively, and  $\Delta$  denotes the noninferiority margin of 1.5 mmHg or 1.0 mmHg as specified below.

The primary analysis of the primary efficacy endpoint will be performed using a MMRM of IOP based on the FAS. A separate MMRM will be used for IOP at each scheduled timepoint (8:00, 10:00, or 16:00). For each scheduled timepoint, the model will include treatment ( $T_i$ ), analysis visit ( $V_j$ ), and treatment-by-visit interaction ( $TV_{ij}$ ) as fixed effects, and baseline IOP at the scheduled timepoint as a covariate. Correlations of IOP measurements within-subject will be modeled using an unstructured covariance matrix. The mathematical model is given by:

$$IOP_{ijn} = \mu + T_i + V_j + TV_{ij} + \varepsilon_{ijn}$$

where  $\mu$  denotes the overall mean, and  $\varepsilon$  denotes the random error associated with the individual subject. The above model allows treatment effect and its variability to vary over study visits.

If there are convergence issues, covariance matrix structures other than unstructured will be tried in the following order: (1) heterogeneous Toeplitz (TOEPH), (2) heterogeneous autoregressive of order 1 (ARH(1)), (3) heterogeneous compound symmetry (CSH), and (4) compound symmetry (CS). The first covariance structure that converges will be used as the primary analysis. Least squares mean IOP values for each treatment arm and differences between least squares treatment arm means and associated 95% confidence intervals will be reported for each of the nine timepoints.

The primary analysis will be repeated on pediatric subjects.

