**Noninferiority criteria for primary endpoint:** With respect to the primary study objective, noninferiority of DE-117 to Timolol is achieved if the upper limit of the two-sided 95% confidence interval for the difference in the mean IOP (DE-117 minus Timolol) is  $\leq 1.5$  mmHg at all nine timepoints and  $\leq 1.0$  mmHg at a majority (five or more) of the nine timepoints.

Superiority of DE-117 to Timolol for the primary efficacy endpoint is achieved if the upper limit of the two-sided 95% confidence interval for the difference in the mean IOP (DE-117 minus Timolol) is  $< 0$  mmHg at all nine timepoints.

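### The 90% power is stated for the 1.5 mmHg margin only; no power is given for the two-part success rule, where it is about 72% if 4.0 mmHg is the SD of the quantity analysed

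*Protocol*

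**What the plan says.** **Sample size.** Protocol 14.3.1 uses a two-sided 5% error rate, a 1.5 mmHg margin and a true difference of 0, and concludes that "approximately 400 adult subjects in total (200 subjects per treatment arm) will provide 90% power to demonstrate non-inferiority". The synopsis gives the same inputs: "a standard deviation (SD) of 4.0 mmHg, and a correlation coefficient of 0.6 among repeated measures, approximately 400 adult subjects in total". SAP 3.3 repeats them and adds a source: "The standard deviation of 4.0 mmHg was determined from previous DE-117 studies conducted in the United States", namely studies 33-002 and 33-003.

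**Success rule.** Protocol 14.3.2 requires that the upper limit of the 95% interval "is ≤ 1.5 mmHg at all nine time points and ≤ 1.0 mmHg in majority (5 or more) of the time points". The synopsis and Protocol 14.7.1 say the same. SAP 8.1.1.1.1 keeps both conditions, the second being an upper limit of at most 1.0 "mmHg at a majority (five or more) of the nine timepoints".

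**Model.** SAP 8.1.1.1.1 fits a separate MMRM for each clock time, with "baseline IOP at the scheduled timepoint as a covariate".

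**Not stated.** The documents do not say:
- what the power is under the 1.0 mmHg condition, or how many timepoints the 90% covers jointly;
- whether 4.0 mmHg is a raw, change-score or baseline-adjusted SD;
- whether the 0.6 includes the correlation with baseline;
- what attrition was assumed.

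**The concern.** The sample-size text describes an easier target than the one the trial must hit. At a single timepoint with an SD of 4.0 mmHg, the 1.0 mmHg condition is much harder to meet than the 1.5 mmHg condition, and it does not appear in the power statement. A reader would take the risk of missing non-inferiority, when the drugs are truly equal, to be 10%. Under one natural reading of the inputs it is about 28%. Failure on the primary endpoint also closes the fixed sequence in SAP 6.4, so none of the six later tests would be reached. Type I error and the validity of the success rule are not in question.

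**Working it through.** **Inputs.** 200 per arm, SD 4.0 mmHg, correlation 0.6, true difference 0, two-sided 5% (Protocol 14.3.1). Nine timepoints, with both conditions (Protocol 14.3.2). Any attrition rate or baseline correlation used below is an assumption.

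**Step 1: the plan's own figure, one timepoint.** SE = 4.0 × √(2/200) = 0.40 mmHg. Power = Φ(margin/SE − 1.96).
- 1.5 mmHg: Φ(3.75 − 1.96) = 96.3%. For 90%, 150 per arm would be enough.
- 1.0 mmHg: Φ(2.50 − 1.96) = 70.5%.

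Neither figure is 90%.

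**Step 2: joint conditions, with 4.0 mmHg as the SD of the analysed quantity.** I simulated the estimated differences as multivariate normal with mean 0, SE 0.40 and a common correlation of 0.6. The upper limit is the estimate plus 1.96 × SE. With 1,000,000 draws the Monte Carlo error is below 0.05 percentage points.

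| Condition | Power |
|---|---|
| ≤1.5 mmHg at three timepoints jointly | 91.6% |
| ≤1.5 mmHg at all nine | 84% |
| ≤1.0 mmHg at five or more of nine | 75% |
| Both (the success rule) | 72% |

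The nearest match to 90% is three joint timepoints at 1.5 mmHg, which is not the rule. Changing the common correlation does not help: the full rule gives 67% at 0, peaks at about 73% near 0.7, and is 71% at 0.95. With an assumed 10% lost at all visits (180 per arm), it is 66%.

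**Step 3: 4.0 mmHg as the raw SD, analysed with baseline as a covariate.** Let r be the correlation of each follow-up value with one common baseline. Then residual SD = 4.0 × √(1 − r²), and residual correlation = (0.6 − r²)/(1 − r²). For r = 0.6 these are 4.0 × √0.64 = 3.20 mmHg and 0.24/0.64 = 0.375.

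| r | Residual SD (mmHg) | Residual correlation | Full rule, 200 per arm |
|---|---|---|---|
| 0.3 | 3.82 | 0.56 | 78% |
| 0.4 | 3.67 | 0.52 | 82% |
| 0.5 | 3.46 | 0.47 | 88% |
| 0.54 | 3.37 | 0.44 | 90% |
| 0.6 | 3.20 | 0.375 | 94% |

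An assumed 10% loss at all visits lowers the r = 0.6 case to about 90.5%. Giving each clock time its own baseline changes these figures little: about 82% at 0.4, 88% at 0.5 and 95–96% at 0.6.

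**Step 4: what 90% requires.** With 200 analysed per arm, the full rule reaches 90% at a residual SD of about 3.3 mmHg if the residual correlation is 0.6, and about 3.4 mmHg if it is 0.4.

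**The case against.** The strongest reply is that the 90% may be right. The endpoint is IOP itself and the text says SD without the word residual, so a raw SD is at least as natural a reading. If the 0.6 among repeated measures also covers baseline, the planned model gives about 94% for the full rule, and about 90.5% after a 10% loss. A correlation is not needed for a single-timepoint calculation, so quoting one suggests that the timepoints were treated jointly. All of this stands. It is why a reader should not infer that the 90% is wrong, that it cannot be obtained from the stated figures, or that the trial is underpowered. But the favourable reading needs two facts that neither document states: that 4.0 mmHg is raw, and that the 0.6 extends to baseline. Naming one margin does not prove that the second was ignored, but nothing shows that it was included.

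Two smaller replies carry less weight. Pediatric subjects would enter the primary set, since "The Full Analysis Set (FAS) will include all randomized subjects who received at least one dose of study medication" (with IOP data at baseline and afterwards). Counting 15 more per arm at the same assumed SD raises 72% only to 76%, and the power claim is made for adults. Attrition may be below 10%: Protocol 8.5 encourages visits up to Visit 5 after study drug is stopped, and SAP 6.2.1 censors IOP only after non-study IOP-lowering therapy. That affects the allowance for loss, not the 72%, which is before attrition.

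**Conclusion.** The concern holds as a gap in a stated design figure. The 90% is attached to one margin, and the rule that decides the trial has two. Taking 4.0 mmHg directly as the SD of the analysed quantity, power is about 84% for the named margin at all nine timepoints and about 72% for the full rule, before attrition. Taking it as a raw SD with baseline adjustment, power runs from about 82% to 94% as the baseline correlation goes from 0.4 to 0.6, and passes 90% at about 0.54. These are scenarios, resting on a true difference of 0, normal estimates and a common correlation. The choice between them depends on data from studies 33-002 and 33-003 that the documents do not show. So the arithmetic supports no stronger claim than this: power for the actual rule is unstated, and under one plain reading it is well below 90%.

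**What to change.** Simulate power for the full two-part rule under the planned baseline-adjusted MMRM for each clock time. Use the residual SD and residual correlation from studies 33-002 and 33-003, and a stated attrition rate. Restate the result in Protocol 14.3.1, the synopsis and SAP 3.3, naming both margins, the nine timepoints, the basis of the SD, whether the correlation includes baseline, and whether pediatric subjects count in the analysed number.

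Keep 90% only if that simulation gives at least 90%; the residual SDs in Step 4 are for orientation, not a pass mark. Otherwise state the simulated figure. If 4.0 mmHg proves to be the residual SD, the text could read: With 200 adult subjects per arm, a true difference of 0 mmHg, a baseline-adjusted SD of 4.0 mmHg and a correlation of 0.6, simulated power to meet both non-inferiority conditions is about 72% before attrition.

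The cost is one simulation and a few sentences in three places, and the stated power may become less favourable. Enrolment, the success rule and the analysis stay as they are.
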